15. During Screening, any of the following per central laboratory (tests may be repeated once within the same Screening Period to confirm results prior to Randomization):
 - Aspartate aminotransferase $> 2.5 \times$ upper limit of normal (ULN)
 - Alanine aminotransferase $> 2.5 \times$ ULN
 - Total bilirubin $> 1.5 \times$ ULN (unless due to Gilbert's syndrome)
 - Serum IgG $< 600 \text{ mg/dL}$ (or $< 6 \text{ g/L}$) or $< 400 \text{ mg/dL}$ ($< 4 \text{ g/L}$) if due to active SLE/LN
 - Neutrophil count $< 1000/\mu\text{L}$ (or $< 1.0 \times 10^9/\text{L}$) or $< 500/\mu\text{L}$ ($< 0.5 \times 10^9/\text{L}$) if due to active SLE
 - Platelet count $< 50,000/\mu\text{L}$ (or $< 50 \times 10^9/\text{L}$) or $< 25,000/\mu\text{L}$ ($< 25 \times 10^9/\text{L}$) if due to active SLE
 - Hemoglobin $< 8 \text{ g/dL}$ (or $< 80 \text{ g/L}$) or $< 7 \text{ g/dL}$ ($< 70 \text{ g/L}$) if due to active SLE
 - Glycosylated hemoglobin $> 8\%$ (or > 0.08)
 - Total lymphocyte count $< 200 \text{ cells/mm}^3$
16. Confirmed positive test for hepatitis B serology defined as:
 - Hepatitis B surface antigen, or
 - Hepatitis B core antibody (HBcAb) and hepatitis B virus (HBV) DNA detected above the lower limit of quantitation (LLOQ) by reflex testing by the central laboratory at Screening.Note that participants who are HBcAb positive at Screening will be tested every 3 months for HBV DNA. IP will be discontinued if the participant's HBV DNA levels are confirmed to exceed the LLOQ as per the central laboratory.
17. Positive test for hepatitis C virus antibody unless documented as having had successful treatment of active hepatitis C infection.
18. Active tuberculosis (TB), or a positive IFN-gamma release assay (IGRA) test at Screening, unless documented history of appropriate treatment for active or latent TB.
Note that participants with an indeterminate IGRA test result with well-documented

previous treatment do not need to repeat testing and are eligible for randomization. Participants with an indeterminate IGRA test result can repeat the test, but if the repeat test is also indeterminate, they are excluded.

19. Any severe herpes virus family infection (including Epstein-Barr virus, cytomegalovirus [CMV]) at any time prior to Randomization, including, but not limited to, disseminated herpes, herpes encephalitis, recent recurrent herpes zoster (defined as 2 episodes within the last 2 years), or ophthalmic herpes.

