APPENDIX 2 STUDY-SPECIFIED OPPORTUNISTIC INFECTIONS

Definite ^{a,b} Opportunistic Infection	Probable ^c Opportunistic Infection
Pneumocystis jirovecii	Paracoccidioides infections
BK virus disease, including polyomavirus-associated nephropathy	Penicillium marneffei (talaromycetes)
CMV disease	Sporothrix schenckii
Post-transplant lymphoproliferative disorder (EBV)	Cryptosporidium species (chronic disease only)
Progressive multifocal leukoencephalopathy	Microsporidiosis
Bartonellosis (disseminated disease only)	Leishmaniasis (visceral only)
Blastomycosis	Trypanosoma cruzi infection (Chagas's disease) (disseminated disease only)
Toxoplasmosis	Campylobacteriosis (invasive disease only)
Coccidioidomycosis	Shigellosis (invasive disease only)
Histoplasmosis	Vibriosis (invasive disease due to Vibrio vulnificus)
Aspergillosis (invasive disease only)	HCV progression
Candidiasis (invasive disease or pharyngeal)	
Cryptococcosis	
Other invasive fungi: Mucormycosis (zygomycosis) (Rhizopus, Mucor, and Lichtheimia), Scedosporium/Pseudallescheria boydii , Fusarium	
Legionellosis	
Listeria monocytogenes (invasive disease only)	
TB	
Nocardiosis	
Non-tuberculous mycobacterium disease	
Salmonellosis (invasive disease only)	
HBV reactivation	
Herpes simplex (invasive disease only)	
Herpes zoster (any form)	
Strongyloides (hyperinfection syndrome and disseminated forms only)	

CMV = cytomegalovirus; EBV = Epstein-Barr virus; HBV = hepatitis B virus; HCV = hepatitis C virus; TB = tuberculosis.

[figure not shown]
Source: [Winthrop et al, 2015](#).

^a Generally does not occur in the absence of immunosuppression, but whose presence indicates a potential or likely alteration in host immunity.

^b Can occur in patients without recognized forms of immunosuppression, but whose presence indicates a potential or likely alteration in host immunity.

^c Published data are currently lacking, but expert opinion believes that risk is likely elevated in the setting of biologic therapy.

APPENDIX 3 2019 EUROPEAN LEAGUE AGAINST RHEUMATISM/AMERICAN COLLEGE OF RHEUMATOLOGY CLASSIFICATION SYSTEM FOR SYSTEMIC LUPUS ERYTHEMATOSUS

$\beta 2\text{GP}1 = \beta 2\text{-glycoprotein 1}$; C = complement; dsDNA = double-stranded DNA; Hep-2 = human epithelial type 2 cells; SLE = systemic lupus erythematosus. Source: [Aringer et al, 2019](#).

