To characterize the PK and immunogenicity of daxdilimab in participants with active, proliferative LN.	
Serum concentration of daxdilimab over time.Rate of ADA directed against daxdilimab and ADA titer for the duration of the study.

Table 1 Trial Objectives and Endpoints

To evaluate the safety and tolerability of daxdilimab in combination with SOC in participants with active, proliferative LN.	
Incidence of treatment-emergent adverse events (TEAEs) over time.Incidence of treatment-emergent serious adverse events (TESAEs) over time.Incidence of treatment-emergent AEs of special interest (TEAESIs) over time: hypersensitivity reaction, including anaphylaxis, severe (Grade 3 or higher) viral infection/reactivation, herpes zoster, opportunistic infection, and malignancy (except non-melanoma skin cancer).
[REDACTED]	[REDACTED]

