SAEs and TEAEs will be summarized descriptively by treatment group and overall. Percentages will be based on the number of treated participants in the safety set within a treatment group and overall. Tables will be sorted by descending frequency of SOC and by descending frequency of PT within an SOC. Specific AEs will be counted once for each participant for calculating rates, but all events will be presented in participant listings. Listings will be provided for all TEAEs and non-treatment-emergent AEs.

TESAEs will be summarized by serious adverse event (SAE) criteria as well.

The following definitions will be used for AEs:

- **Treatment-emergent adverse event (TEAE):** Any AE with an onset on or after the first dose of study intervention
- **Treatment-emergent SAE (TESAE):** A TEAE that is serious. The details are referenced in Section 8.3.1.3 of protocol

A table will show the number and percentage of participants with at least one event in any of the following categories overall as well as by SOC and PT:

- TEAE
- Treatment-emergent serious adverse event (TESAE)
- TEAE resulting in death
- CTCAE Grade 3 or higher TEAE
- TEAE leading to discontinuation of trial intervention
- Serious and/or grade 3 or higher TEAE
- Trial intervention related TEAE
- Trial intervention related TESAE

An AE of special interest (AESI) is an AE of scientific and medical interest specific to the understanding of the trial intervention and may require close monitoring and collection of additional information by the Investigator. AESIs for this protocol include:

- Hypersensitivity reaction, including anaphylaxis
- Severe viral infection/reactivation (CTCAE v5.0 Grade 3 or higher)
- Opportunistic infection as listed in protocol appendix 2
- Malignancy (except non-melanoma skin cancer)

Treatment emergent AESIs will be summarized by type of AESI as listed above as well as SOC and PT.

Anaphylaxis will be searched using the NIAID (Sampson et al. 2006). The hypersensitivity reactions will be defined using Standardized MedDRA Queries (SMQ): hypersensitivity (narrow). Severe viral infection will be searched using MedDRA HLGT of Viral infectious disorders. Viral reactivation will be searched using MedDRA HLT Hepatic viral infection. Malignancy will be searched using MedDRA SMQ Malignant tumors. All will be described in the Statistical Programming Plan (SPP).

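### Herpes zoster is a named item of the secondary safety endpoint but has no AESI row of its own, and the stated search for viral reactivation is limited to a hepatic term

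*SAP*

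**What the plan says.** **Endpoint.** The Protocol Synopsis, Protocol Section 3 and SAP Section 2.1 (Table 1) define one secondary safety endpoint as the incidence of treatment-emergent AESIs. After hypersensitivity, the list continues: "severe (Grade 3 or higher) viral infection/reactivation, herpes zoster, opportunistic infection, and malignancy (except non-melanoma skin cancer". Zoster and opportunistic infection are separate items.

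**AESI definition.** Protocol 8.3.1.4 and SAP 4.9.1 each list four types: hypersensitivity, severe viral infection or reactivation, opportunistic infection, and malignancy. SAP 4.9.1 words the second as "Severe viral infection/reactivation (CTCAE v5.0 Grade 3 or higher" and the third as "Opportunistic infection as listed in protocol appendix 2". Among the definite opportunistic infections, Protocol Appendix 2 lists "Herpes zoster (any form".

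**Tabulation.** SAP 4.9.1: "Treatment emergent AESIs will be summarized by type of AESI as listed above as well as SOC and PT". The same section counts a participant once within each category, the categories being overall, system organ class and preferred term.

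**Searches.** For severe viral infection: "Severe viral infection will be searched using MedDRA HLGT of Viral infectious disorders". For reactivation: "Viral reactivation will be searched using MedDRA HLT Hepatic viral infection". SAP 4.9.1 names no search for opportunistic infection and refers the details to the Statistical Programming Plan.

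**The concern.** An endpoint that the plan names should come out of the tables that the plan specifies. Here the endpoint has five items and the reporting list has four. The missing one, zoster, sits inside another item from which the endpoint separates it. A reader of the study report who looks for the proportion of participants with zoster in each arm would have to rebuild it from preferred-term rows. A reader of the opportunistic-infection row could not tell shingles from, say, invasive fungal disease or tuberculosis.

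The reactivation search raises a second, smaller issue. The protocol's interest in latent viruses extends beyond the liver. Exclusion criterion 19 bars "Any severe herpes virus family infection (including Epstein-Barr virus, cytomegalovirus [CMV]) at any time prior to Randomization", criterion 20 covers unresolved zoster, CMV and Epstein-Barr infection, and Appendix 2 includes CMV disease, zoster and invasive herpes simplex as well as HBV reactivation. A hepatic term does not match that scope.

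Viral infection and reactivation are among the important potential risks in Protocol 2.2.1, so these are rows that safety readers will look at.

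**Working it through.** No arithmetic in the plan bears on this point. The check sets the lists side by side and traces where each kind of event would be counted.

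**Step 1: endpoint list against AESI list.**

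| Endpoint item (Protocol 3; SAP Table 1) | Own type in Protocol 8.3.1.4 and SAP 4.9.1? |
|---|---|
| Hypersensitivity, including anaphylaxis | Yes |
| Viral infection or reactivation, Grade 3 or higher | Yes |
| Herpes zoster | **No** |
| Opportunistic infection | Yes (Appendix 2, which contains zoster) |
| Malignancy except non-melanoma skin cancer | Yes |

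Four of five items have a row. The gap is the same in both documents, so the SAP has not departed from the protocol. Each document's endpoint list disagrees with its own AESI list.

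**Step 2: where each event goes.**

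| Event | Row it reaches | Route |
|---|---|---|
| Zoster, any grade | Opportunistic infection; also visible by preferred term | Appendix 2 |
| Zoster, Grade 3 or higher | As above, and the combined viral row | Appendix 2; broad viral HLGT |
| CMV, Epstein-Barr or simplex event, Grade 3 or higher | Combined viral row | Broad viral HLGT |
| HBV reactivation | Opportunistic infection; also the combined viral row if Grade 3 or higher | Appendix 2; hepatic HLT |
| Non-hepatic reactivation, identified as reactivation | None | Not reached by the hepatic HLT |

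Only the last line has no destination. It concerns the label of the event, not whether a Grade 3 or higher event is counted.

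**Step 3: does the preferred-term table supply the zoster incidence?** Suppose zoster events code to two preferred terms, with *a* participants under one and *b* under the other. Because a participant is counted once per preferred term, the number with any zoster lies between max(*a*, *b*) and *a* + *b*. The table does not say where. If every event codes to one term, the count is exact, but the plan does not ensure this. The system organ class row is too broad to help.

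**Step 4: can opportunistic infection without zoster be recovered?** Let *n* be the participants in the opportunistic-infection row and *z* those with any zoster. A participant can have both zoster and another Appendix 2 infection. The number with a non-zoster opportunistic infection is therefore *n* − *z* plus those with both, and the planned tables do not give the overlap. Participant listings would give it, but that is reconstruction after the fact.

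**The case against.** The strongest reply is that nothing is lost and little is hidden. Counting shingles as opportunistic infection follows the protocol's own Appendix 2. AESIs are also shown by preferred term with each participant counted once, all TEAEs are tabulated the same way, and every event is listed. The reactivation search feeds a row that combines infection with reactivation, and the broad viral HLGT fills that row with Grade 3 or higher events whether new or reactivated. The tables are descriptive, with no formal hypothesis. The Statistical Programming Plan, which was not available, may already hold the detail.

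Most of this stands, and it rules out several stronger readings that a reader might infer:

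- *Zoster is counted in the wrong place.* It is counted where Appendix 2 puts it. What is missing is a row of its own.
- *The reactivation count is hepatitis only, or severe herpes events are missed.* The SAP plans no separate reactivation count, and on its wording the HLGT brings those events into the combined row.
- *The plan mishandles the drug's main expected risk.* Protocol 2.2.1 gives viral infection and reactivation as one of several important potential risks, does not rank them, and says that no adverse drug reaction has been identified.
- *The malignancy search ignores the non-melanoma exclusion.* The AESI definition in SAP 4.9.1 already carries it, and the sentence naming the search tool does not override it.

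Exclusion criteria 19 and 20 are eligibility rules and do not define a reactivation outcome. They show the breadth of the protocol's interest, no more.

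The reply does not remove the endpoint gap. Preferred-term rows do not guarantee one zoster incidence (step 3), and a programming plan should not have to settle which endpoint items are reported when the SAP itself fixes four.

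**Conclusion.** The point holds as a mismatch between a named endpoint and its planned tabulation. One of the five items in the TEAESI endpoint has no grouped participant-level incidence, and the opportunistic-infection row merges two items that the endpoint keeps apart. The hepatic-only reactivation search is a poorly chosen rule, but it costs only the ability to label non-hepatic events as reactivation. It removes no Grade 3 or higher event from the combined row.

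The documents give no expected rate of zoster or of other Appendix 2 infections, so no count of affected participants or share of the row can be derived. Efficacy analyses and type I error are untouched. The change is nonetheless worth making before unblinding, because a stated endpoint should be delivered by its own table and the cost is very small.

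Three assumptions matter. First, the coverage of the MedDRA terms was judged from their names in the SAP. Second, the Grade 3 threshold is read as applying to both infection and reactivation, as the wording of the combined type suggests. If reactivation of any grade was meant, the narrow search would matter more. Third, the Statistical Programming Plan may contain further detail, but SAP 4.9.1 states both the four types and the hepatic term.

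**What to change.** In SAP 4.9.1:

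1. Add herpes zoster (any form, any grade) as its own AESI row, counting each participant once across all zoster preferred terms, in each of the period tables (Stage I, Stage II, any daxdilimab exposure).
2. Show opportunistic infection with and without zoster.
3. Before unblinding, state the list of terms used to find Appendix 2 infections.
4. Before unblinding, extend the reactivation terms beyond the hepatic HLT to the herpes-family viruses that the protocol names.

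In Protocol 8.3.1.4, align the AESI list with the endpoint in Section 3 so that both documents carry the same items.

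The cost is a few extra table rows, wording changes in the SAP, programming plan and protocol, and a short review of the term lists. No new data are needed.

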4.9.2 Additional Safety Assessment

4.9.2.1 Clinical laboratory Evaluations

Laboratory assessments are defined in Section 8.2.4 of Protocol. All protocol-required laboratory tests must be conducted in accordance with the laboratory manual and the Schedule of Activities (SoA). Any clinically significant value will be reported as an AE. The laboratory results must be retained with source documents.

Clinical laboratory evaluations will be summarized for each treatment group and overall. The summary of clinical laboratory data will be generated for the Stage I data based on the Safety Analysis Set, and for the Stage II data based on Stage II Analysis Set. For analysis purposes, laboratory results based upon standardized units will be used. All data will be presented in listings, and a specific listing of abnormal results will be provided.

The following summary will be provided for hematology and biochemistry and lipid profile by treatment groups:

- Observed values and changes from the baseline by visit
- Worst toxicity grade
- At least 2-grade shift from baseline to worst toxicity
- Shift from the baseline relative to the normal range

In addition, the number and percentage of participants with the following liver-related abnormalities will be summarized if the following criteria is met at any post-baseline visit:

- AST or ALT: (a) $\geq 3 \times$ ULN; (b) $\geq 5 \times$ ULN; (c) $\geq 8 \times$ ULN
- Total bilirubin: $\geq 2 \times$ ULN

- ALT or AST $\geq 3 \times$ ULN and total Bilirubin $\geq 2 \times$ ULN
- ALT or AST $\geq 5 \times$ ULN for more than 2 weeks

The following summary will be provided for urinalysis by treatment groups:

- Observed values and changes from the baseline by visit
- Shift from the baseline relative to the normal range

4.9.2.2 Vital Signs

The observed values, along with the changes from baseline, will be summarized at each time point by treatment for systolic blood pressure, diastolic blood pressure, body temperature, heart rate, and respiratory rate. A listing of vital signs will be presented by treatment, patient, vital sign, and visit.

In addition, a summary of participants with clinically significant vital signs values (meeting any of following criteria) will also be provided. The summary of vital signs will be generated by visit using the safety analysis set for Stage I and Stage II.

- Systolic blood pressure: < 90 mmHg, > 160 mmHg
- Diastolic blood pressure: < 60 mmHg, > 100 mmHg
- Heart rate: < 50 beats/min, > 100 beats/min
- Respiratory rate: < 12 breaths/min, > 23 breaths/min
- Temperature: $< 36^\circ\text{C}$, $> 38^\circ\text{C}$

4.9.2.3 Prior and Concomitant Medications

Prior and concomitant medications and procedures will be summarized using the safety analysis sets accordingly. The details of prior and concomitant medications are described in Section 6.7 of the protocol.

Medications collected at Screening and during the trial will be coded using the current version of the World Health Organization Drug dictionary (WHO-DD). Number (%) of participants who received prior medications and concomitant medications will be summarized by treatment presented by WHO-DD Anatomical Therapeutic Chemical (ATC) category and PT. At each level of summarization, a participant is counted once if the participant reported one or more medications at that level. The summary of prior and concomitant medications during Stage I will be based on safety analysis set. The concomitant medications during Stage II will be summarized based on the second-year analysis set. The prior and concomitant medications are defined as below.

- Prior medications are defined as medications with a stop date occurring before the first trial intervention administration date.

- Concomitant medications during Stage I are defined as follows:
 - Medications with a start date before Week 64 trial intervention administration and stop date on or after the first trial intervention administration date for the participants entering the second-year treatment period.
 - Medications with stop date on or after the first trial intervention administration date for participants not entering the second-year treatment period.
- Concomitant medications for Stage II are defined as medications with a stop date on or after Week 64 daxdilimab administration date.

Rescue therapy for worsening LN may be administered at the discretion of Investigators as clinically indicated. Final rescue therapy will be reviewed and determined before unblinding at the end of Stage I.

Rescue therapy includes:

The initiation of any new treatment for lupus or LN with the selected restricted medications or prohibited medications as a rescue. Participants who receive rescue therapy will be considered treatment failures for subsequent endpoint analyses (such as CRR). Detailed prohibited medications are defined in the protocol Section 6.7.2, restricted medications are defined in the protocol Section 6.7.3, and rescue medicine is defined in the protocol Section 6.7.6. Additionally, certain other concomitant medications initiated after randomization beyond those allowed in protocol Section 6.7.5 may also constitute rescue therapy.

The number and percentage of participants who received rescue therapy will be summarized by treatment group according to the defined criteria using the Safety Analysis Set for Stage I and using Stage II Analysis Set for Stage II by WHO-DD ATC category and PT set.

- New Treatment

The number and percentage of participants who received the new treatment will be summarized.

- MMF/MPA

The number and percentage of participants who received MMF/MPA at above allowed dose by the time window will be summarized.

- Corticosteroids

The number and percentage of participants who received corticosteroids beyond the one allowed steroid bursts, increases in corticosteroids for the prevention of adrenal insufficiency, or during the required stable dose time window from baseline will be summarized.

4.9.2.4 Electrocardiogram Results

12-lead ECGs will be performed as a safety assessment at the visits specified in Section **Error! Reference source not found.** of protocol. Any clinically significant value will be reported as an AE.

The observed values, along with the changes from baseline, will be summarized at baseline and each postbaseline time point for ventricular heart rate, PR interval, QRS duration, QT interval, and the corrected QT interval (QTc) using the safety analysis. The number (%) of participants meeting the following criteria will be summarized:

- QTc > 450 msec
- QTc > 480 msec
- QTc > 500 msec
- QTc increases from baseline > 30 msec
- QTc increases from baseline > 60 msec

Corrected QT (QTc) intervals will be derived using Fridericia's correction (QTcF) and Bazett's correction (QTcB). In addition, the overall clinical evaluation of electrocardiogram results (normal, abnormal, not clinically significant abnormal, clinically significant abnormal) will also be summarized. The summary will be produced using the Safety Analysis Set for the overall study.

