4 STATISTICAL METHODS

4.1 General Considerations for Data Analyses

All statistical calculations will be primarily performed using SAS® System Version 9.4 or higher (SAS Institute Inc., Cary, NC, USA).

The primary comparison will be between the daxdilimab [REDACTED] mg or [REDACTED] mg group and the placebo group. For primary and second efficacy analyses, the data up to the [REDACTED] Visit will be used. The applied methods for statistical descriptive analysis and presentations will be based on the types of variables being tested.

- 1) Overall summary of descriptive statistics for continuous variables will include, not limited to, the number of observations, mean, standard deviation, median, minimum, and maximum, first quartile, and third quartile values in each treatment group
- 2) Overall summary of descriptive statistics for categorical variables will include, not limited to, frequency counts, percentage of patients or point estimate

Data summaries for Stage I of the Treatment Period will be presented by randomized treatment group (i.e., “daxdilimab [REDACTED] mg”, “daxdilimab [REDACTED] mg” and “Placebo”) and overall. Data summaries for Treatment Period Stage II (i.e., the Stage II period beginning at the [REDACTED] Visit) will be presented according to the reassigned treatment regimen with respect to achievement of PRR (or CRR) at Weeks 48 and maintained through Week 52 (e.g., “daxdilimab [REDACTED] mg [REDACTED] mg [REDACTED]”, “daxdilimab [REDACTED] mg [REDACTED] mg [REDACTED]”, “Placebo [REDACTED]/Placebo [REDACTED]”, and “Placebo [REDACTED]/daxdilimab [REDACTED] mg [REDACTED]”). For the longitudinal analysis covering two-stage periods (Stage I and Stage II) of treatment, participants will be analyzed according to the combination of treatment that they actually received in Stage I and Stage II treatment period.

Summaries of study and participant characteristics (e.g., demographics and baseline characteristics, medical history, protocol deviations) will be reported.

For additional details on data presentation, refer to the Statistical Programming Plan (SPP).

Table 4 provides the overview of the study periods for reporting purposes. All major analysis endpoints will be reported for Stage I and Stage II. All assessments, unless otherwise specified, will be included in by-patient listings. Data collected at unscheduled visits may be used in the data analysis and will not be presented in the summary statistics report.

Table 4 Study Periods

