4.4.2 Safety Analysis Set

Safety Analysis Set will include all participants who receive any dose of trial intervention in the study. Participants will be analyzed according to the treatment that they actually received. Safety, PD, and ADA analyses will be based on the Safety Analysis Set.

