4.15 Final Analysis

The final analysis will be conducted after all participants have completed the Week 112 Visit or discontinued early from the study.

By study design, the participants may undergo the different [REDACTED] based upon the renal response observed at Week 48 and Week 52. Thus, in the final analysis, the participants will be divided into two subgroups based on their PRR/CRR status at the Week 48 through Week 52:

- PRR/CRR Subgroup: Participants who achieved PRR or CRR at Week 48 and sustained through Week 52 will remain in their treatment groups. Statistical modeling can be used to examine the treatment effect between treatment groups over the Stage II of treatment (i.e., [REDACTED] mg [REDACTED] vs. placebo and [REDACTED] mg [REDACTED] vs. placebo), as applicable. All endpoints defined in primary, secondary and [REDACTED] will be analyzed. Some key endpoints examples are highlighted below.
- Non-PRR/CRR Subgroup: Participants who did not achieve PRR or CRR at either [REDACTED] will be administered daxdilimab [REDACTED] mg SC [REDACTED] through [REDACTED] (last dose administered at [REDACTED]). The final analysis for this subgroup will be descriptive only. No statistical modeling will be performed and no formal statistical comparison between treatment groups will be tested. All endpoints defined in primary, secondary and [REDACTED] except for all time-to-event endpoints, will be analyzed. Some key endpoints examples are highlighted below.

In the final analysis, all analyses planned for the primary analysis will be rerun with the Full Analysis Set.

For the non-PRR/CRR subgroup, the following analyses up to the Week 112 visit will be covered in the final analysis using Stage II Analysis Set:

- Proportion of participants achieving PRR or CRR or [REDACTED] in the Stage II
- Change from baseline in eGFR. In addition, change from re-baseline (Week 64) in eGFR will be explored descriptively
- Change from baseline in UPCR. In addition, change from re-baseline (Week 64) in UPCR will be explored descriptively

- Proportion of participants with prednisone-equivalent dose ≤ 2.5 mg/day for participants with baseline OCS > 2.5 mg/day until Week 92

■ [REDACTED]
■ [REDACTED]
■ [REDACTED]

For the PRR/CRR subgroup, the following analyses using the data up to the Week 112 visit will be covered in the final analysis using Stage II Analysis Set:

- Proportion of participants sustaining PRR or CRR or [REDACTED] in the Stage II

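### SAP 4.9.2.4 sets no Stage I/Stage II split for the QTc threshold counts and overall ECG evaluation, so whole-study counts can mix placebo and daxdilimab time

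*SAP*

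**What the plan says.** SAP 4.9.2.4 contains three kinds of ECG output:

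- Observed values and changes from baseline, including QTc, which "will be summarized at baseline and each postbaseline time point for ventricular heart rate, PR interval, QRS duration, QT interval".
- QTc threshold counts: "The number (%) of participants meeting the following criteria will be summarized". No visit, stage or treatment column is attached to them.
- An overall clinical evaluation (normal, abnormal and so on).

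The section then ends: "The summary will be produced using the Safety Analysis Set for the overall study".

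The laboratory section (SAP 4.9.2.1) differs: its summary is "generated for the Stage I data based on the Safety Analysis Set, and for the Stage II data" on the Stage II Analysis Set. Vital signs (SAP 4.9.2.2) are summarised by visit for Stage I and Stage II. Under SAP 4.4.2, "Participants will be analyzed according to the treatment that they actually received. Safety, PD, and ADA analyses will be based on the Safety Analysis Set". No rule there covers a participant who received placebo and later daxdilimab.

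Such participants will exist. SAP 4.15 gives daxdilimab in Stage II to "Participants who did not achieve PRR or CRR at either" of the assessment visits, and it lists a placebo-to-daxdilimab pathway. Week 64 as the first Stage II dose is visible in SAP 4.9.2.3: "Concomitant medications for Stage II are defined as medications with a stop date on or after Week 64 daxdilimab administration date".

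**The concern.** A threshold count is made per participant: one QTc value above the limit at any time puts that person in the numerator. If the period is the whole study, a placebo participant who switches can enter the numerator because of an ECG recorded on daxdilimab. Counted under placebo, that event narrows the contrast with daxdilimab. Counted under daxdilimab, placebo-time ECGs enter the daxdilimab column.

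The combination columns in SAP 4.1 do not remove the problem. For analyses that span both stages, "participants will be analyzed according to the combination of treatment that they actually received in Stage I and Stage II treatment period". A placebo/placebo column then holds only responders, and a placebo/daxdilimab column holds only non-responders and still pools both periods within each person.

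The Week 52 primary analysis is exposed as well. SAP 3.2 includes all safety data collected before the cut-off, and by then early enrollees may already have ECGs from after Week 64.

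**Working it through.** The plan gives no ECG or QTc rate, so there is no figure of its own to reproduce. The check is a comparison of texts, followed by an illustration of size.

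**1. Is the overall study a separate period in this SAP?** Yes. SAP 4.6 summarises exposure for Stage I, for Stage II and for the overall study. SAP 4.13 summarises ADA for Stage I on one analysis set and for the overall study on another. Read consistently, 4.9.2.4 asks for one period that covers both stages.

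**2. Which ECGs fall before the switch?** Protocol Table 3 marks post-baseline ECGs at visits 9 and 16. The 24-hour UPCR row of the same table marks visits 2, 6, 9, 12, 15 and 16, and Protocol 8.1 gives the first-year UPCR weeks as 0, 12, 24, 36, 48 and 52. So visit 9 is Week 24 and visit 16 is Week 52, both before Week 64. The first second-year ECG in Protocol Table 4 is at visit 22. Visits there run every four weeks from visit 17 at Week 56, so visit 22 is Week 56 + 5 × 4 = Week 76, after the switch. The positions of the later ECG marks in that table cannot be read reliably in the available text, and nothing here depends on them.

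**3. How many might switch?** SAP 2.3 gives 70 per group and an assumed placebo CRR of 25%. Placebo ORR is not stated. It cannot be below CRR, so 25% is the floor under the design assumption; 65% is an assumed upper value.

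- ORR 25%: 70 × (1 − 0.25) = 52.5
- ORR 65%: 70 × (1 − 0.65) = 24.5

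That is about 24 to 53 of 70, before any loss through early discontinuation.

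**4. What could pooling do?** Let p0 and p1 be the per-stage risk of a QTc outlier on placebo and on daxdilimab. Assume the stages are independent, the risk is the same in each stage, everyone enters Stage II, and counts are shown by first-year group. Then:

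- Placebo, any time = ORR × [1 − (1 − p0)²] + (1 − ORR) × [1 − (1 − p0)(1 − p1)]
- Daxdilimab, any time = 1 − (1 − p1)²

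For p0 = 5% and p1 = 10%, the terms are 1 − 0.95² = 0.0975, 1 − 0.95 × 0.90 = 0.145 and 1 − 0.90² = 0.19.

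- ORR 25%: placebo = 0.25 × 0.0975 + 0.75 × 0.145 = 0.133; ratio = 0.19 / 0.133 = 1.43
- ORR 65%: placebo = 0.65 × 0.0975 + 0.35 × 0.145 = 0.114; ratio = 0.19 / 0.114 = 1.66

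| Assumed p0 vs p1 | Stage I ratio | Whole-study ratio, ORR 25% to 65% | Whole-study ratio, no switching |
|---|---|---|---|
| 5% vs 10% | 2.0 | 1.43 to 1.66 | 1.95 |
| 5% vs 15% | 3.0 | 1.64 to 2.12 | 2.85 |

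The last column shows that the loss comes from switching and not from the longer period. On the difference scale, the 5% vs 10% case gives 0.057 to 0.076 over the whole study, against 0.092 without switching. The Stage I difference is 0.050, lower because it covers one stage only.

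**The case against.** The strongest reply is that the SAP already gives an unmixed ECG comparison with placebo. This stands in part. A reader might infer from the closing sentence of 4.9.2.4 that no clean placebo comparison of ECG data exists. The documents do not support that: values and changes, QTc included, are summarised at each time point, and both first-year ECGs precede Week 64. Only the participant-level threshold counts and the overall evaluation are in question.

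Second, general rules point towards a split. SAP 4.1 presents Stage I data by randomised group and reports major endpoints for both stages. SAP 4.9.1 says that safety data are shown separately by study period. So it would also go too far to read the closing sentence as settling that no Stage I ECG count will be made. But the period table in 4.9.1 is written for adverse-event onset, and 4.9.2.4 gives a specific and different instruction without reconciling the two. A programmer following 4.9.2.4 would produce the pooled table.

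Third, the closing sentence may govern only the overall evaluation named just before it. In that case the threshold counts have no stated period at all, which also needs a sentence.

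Fourth, table specifications sit in the separate Statistical Programming Plan, which may already resolve this. That is possible, but the laboratory and vital-sign sections settle the period in the SAP itself.

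Finally, materiality is limited, and this stands. Safety has no formal hypothesis, QT effects are not among the listed AESIs or the stated potential risks, and clinically significant ECG findings are also reported as adverse events, which are split by stage.

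**Conclusion.** The point holds as a gap in the specification of two ECG outputs. As written, 4.9.2.4 leads to whole-study QTc threshold counts and a whole-study ECG evaluation that mix placebo-time and daxdilimab-time recordings for placebo participants who switch at Week 64. This departs from the laboratory and vital-sign sections and is not reconciled with SAP 4.1 and 4.9.1.

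The size is uncertain. The range of about 24 to 53 switchers rests on an assumed placebo ORR, and the risk ratios rest on assumed outlier rates, independent stages and no dropout. They show the direction, dilution of a difference, and not an expected result. No hypothesis test is affected. The importance is minor, but the correction is cheap and uses data already collected.

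**What to change.** In SAP 4.9.2.4, replace the closing sentence so that the QTc threshold counts and the overall clinical evaluation are produced:

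- for Stage I, on the Safety Analysis Set, using ECGs before the first Stage II dose, by Stage I treatment group; and
- for Stage II, on the Stage II Analysis Set, by treatment pathway.

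An overall-study table may stay as a supplement. The by-visit summaries need no change. The cost is a sentence or two in the SAP and one or two extra table shells, with no new data collection.
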